2. STUDY OBJECTIVES

2.1. Primary Objectives

The primary objective of this study is:

- To determine the effect size of PRM-151 relative to placebo in change from Baseline to Week 28 in mean FVC% predicted, pooling subjects on a stable dose of pirfenidone or nintedanib and subjects not on other treatment for IPF.

2.2. Secondary Objectives

The secondary objectives of this study are:

- Determine the effect size of PRM-151 relative to placebo in change from Baseline to Week 28 in normal lung parenchyma as quantified on high- resolution CT (HRCT) imaging analysis, pooling subjects on a stable dose of pirfenidone or nintedanib with subjects not on other treatment for IPF.
- Determine the effect size of PRM-151 relative to placebo in change from Baseline to Week 28 in mean FVC% predicted, separately in subjects on a stable dose of pirfenidone or nintedanib and in subjects not on other treatments for IPF.
- Determine the effect size of PRM-151 relative to placebo in change from Baseline to Week 28 in normal lung parenchyma as quantified on HRCT imaging analysis, separately in subjects on a stable dose of pirfenidone or nintedanib and in subjects not on other treatments for IPF.
- Assess the tolerability and safety of PRM-151 in subjects with IPF through Week 28.
- Assess the ability of PRM-151 to reduce disease-related events associated with mortality
- Determine the effect size of PRM-151 relative to placebo on pulmonary function in addition to mean change in FVC% predicted
- Determine the effect size of PRM-151 relative to placebo on 6-minute walk distance
- Determine the effect size of PRM-151 relative to placebo on Hb-corrected DLCO.

2.3. Exploratory Objectives

The exploratory objectives of this study are:

- Evaluate the efficacy and estimate the size of effect of PRM-151 relative to placebo in change from baseline to weeks 4, 8, 12, 16, 20, 24 and 28 in FVC % predicted and 6-minute walking distance, pooling subjects on a stable dose of pirfenidone or nintedanib with subjects not on other treatment for IPF and separately in subjects on a stable dose of pirfenidone or nintedanib and in subjects not on other treatments for IPF.
- To assess the impact of PRM-151 on disease related symptoms.
- Assess the impact of PRM-151, disease pathogenesis and disease progression on exploratory serum, cellular and genetic biomarkers

3. STUDY ENDPOINTS

3.1. Primary Endpoint

The primary endpoint for the study is:

- Mean change in FVC % predicted from Baseline to Week 28.

3.2. Secondary Endpoints

The secondary endpoints for the study are:

1. Structural Imaging:

- Mean change from Baseline to Week 28 in total lung volume and volume of parenchymal features on HRCT (in ml and % of total lung volume) representative of interstitial lung abnormalities (ILA), including ground glass density, reticular changes, and honeycombing, using quantitative imaging software.
- Mean change from Baseline to Week 28 in volume of parenchymal features on HRCT (in ml and % of total lung volume) representative of normal lung (non-ILA), including normal and mild low attenuation areas, using quantitative imaging software.
- Correlation between mean change from Baseline to Week 28 in FVC % predicted and mean change from Baseline to Week 28 in total lung volume and volume of parenchymal features on HRCT (in ml and % of total lung volume) representative of interstitial lung abnormalities (ILA), including ground glass density, reticular changes, and honeycombing by quantitative imaging software.

2. Safety: Tolerability/safety will be assessed over the 28-week study period by the following parameters:

- Incidence of AEs.
- Incidence of serious adverse events (SAEs).
- Incidence of respiratory AEs and SAEs.
- Proportion of subjects discontinuing study drug due to AEs.
- Change from Baseline in hematology and serum chemistries.
- All-cause mortality.
- Mortality due to respiratory deterioration.

3. Disease related events associated with mortality: The number of “respiratory decline” events over the 28-week study period as defined below:

- Unscheduled visits to a healthcare professional for respiratory status deterioration.
- Urgent care visits for respiratory status deterioration.
- Hospitalization due to a worsening or exacerbation of respiratory symptoms.

All “respiratory decline” events will be further characterized according to the definitions of IPF-related acute exacerbation, as proposed by an expert committee sponsored by the IPF Clinical Research Network and the National Heart Lung and

Blood Institute (NHLBI) (Collard, Moore et al. 2007) and applied by (Collard, Yow et al. 2013)

- Acute onset of symptoms (< 30 days in duration)
- New radiographic abnormalities (bilateral ground glass or consolidation on HRCT with no pneumothorax or pleural effusion)
- The absence of an identified infectious etiology by routine clinical practice
- Exclusion of alternative causes by routine clinical practice, including:
 - a. Left heart failure
 - b. Pulmonary embolism
 - c. Identifiable cause of acute lung injury

4. Pulmonary Function Tests

- Proportion (%) of subjects with a decline in FVC% predicted of $\geq 5\%$ and $\geq 10\%$ from Baseline to Week 28.
- Proportion (%) of subjects with a decline in FVC in ml of $\geq 100\text{ml}$ and $\geq 200\text{ml}$ from Baseline to Week 28.
- Proportion of subjects with an increase in FVC % predicted of $\geq 5\%$ and $\geq 10\%$ from Baseline to Week 28.
- Proportion of subjects with an increase in FVC in ml of $\geq 100\text{ ml}$ and $\geq 200\text{ ml}$ from Baseline to Week 28.
- Proportion of subjects with stable disease by FVC %, defined as a change in FVC % predicted of $< 5\%$ from Baseline to Week 28.
- Proportion of subjects with stable disease by FVC in ml, defined as a change in FVC of $< 100\text{ml}$ from Baseline to Week 28.
- Mean change from Baseline to Week 28 in % predicted Hb-corrected diffusion capacity of carbon monoxide (DLCO).
- Change in 6-minute walk distance, in meters, from Baseline to Week 28.

3.3. Exploratory Endpoints

The exploratory endpoints for the study include:

1. Other Weeks

- Examine the change from Baseline at Weeks 4, 8, 12, 16, 20, 24 and 28 for the FVC % predicted, FVC in ml, and 6MWT distance.

2. Structural Imaging

- Transitions from Baseline to Week 28 between all categories of lung features (normal, ground glass density, reticular changes, honeycombing, and mild, moderate, and severe low attenuation areas) by quantitative imaging software.
- Correlation of transitions between categories of lung features by quantitative imaging and changes in FVC% predicted.
- Correlation of transitions between categories of lung features by quantitative imaging and changes in Hb-corrected DLCO.
- Impact of inspiratory effort on results of HRCT quantitative imaging.

3. Patient Reported Outcomes

- Change in Patient Reported Outcomes as measured by King's Brief Interstitial Lung Disease Questionnaire (K-BILD) and Leicester Cough Questionnaire (LCQ) from Baseline to Week 28.

4. Biomarkers

- Changes in serum and cellular biomarkers and response according to baseline genetic characteristics: including but not limited to TLR3, L412F polymorphism, and MUC5B promoter polymorphism.

4. INVESTIGATIONAL PLAN

4.1. Overall Study Design and Plan

The current study is a Phase 2, randomized, double-blind, placebo-controlled, pilot study designed to evaluate the efficacy and safety of PRM-151 administered through Week 24 to subjects with IPF. Subjects meeting the eligibility criteria for the study will be randomized to PRM-151 10 mg/kg every 4 weeks or placebo. Efficacy will be evaluated through pulmonary function tests (PFTs), high resolution CT (HRCT), 6-minute walk test (6MWT), and Patient Reported Outcomes (PROs).

Subjects will be evaluated for study eligibility during Screening within 4 weeks before enrollment and Baseline assessments. Subjects who are determined to be eligible, based on Screening assessments, will be enrolled in the study and randomly allocated to treatment with PRM-151 or placebo. Subjects will receive study drug treatment for 24 weeks.

Approximately 117 subjects will be randomly assigned on a 2:1 basis to treatment with PRM-151 or placebo, as follows:

- PRM-151 10 mg/kg IV infusion over 60 minutes on days 1, 3, and 5, then one infusion every 4 weeks
- Placebo IV infusion over 60 minutes on Week days 1, 3, and 5, then one infusion every 4 weeks

The randomization will use a 2:1 ratio (PRM-151: placebo). The randomization will also be stratified according to other treatments for IPF (subjects receiving pirfenidone or nintedanib and subjects with no other treatment for IPF).

After completion of study treatment through Week 24, all subjects may receive PRM-151 10 mg/kg IV infusion over 60 minutes Days 1, 3, and 5, then once every 4 weeks for an indefinite period of time in an open label study extension. Dosing will be administered on Days 1, 3, and 5 will be repeated once every 28 weeks during the extension.

4.1.1. Treatment Period: Efficacy-related Assessments

Subjects undergo testing on an every 4-week basis after randomization (occurring at Weeks 4, 8, 12, 16, 20, 24 and 28) for efficacy and safety.

During treatment, PFTs, 6MWT, and PROs will be performed on an every 4-week basis. HRCT will be performed on Day 1 as the Baseline assessment and again at Week 28. HRCT and PFTs must be done on the same day. PFTs will be reviewed centrally by reviewers blinded to treatment group and time point.

4.1.2. Treatment Period: Tolerability/Safety-Related Assessments

Adverse events (AEs) and concomitant medications will be assessed at all study visits. In addition, information regarding hospitalizations, emergency department visits, and unscheduled or urgent care visits to a health care provider due to a deterioration in respiratory status or symptoms will be collected at all study visits.

4.1.3. Open Label Post-Study Treatment Extension

4.1.4. After completing 24 weeks of treatment, all subjects will be offered the option to receive PRM-151 in an open-label PRM-151 treatment extension period for an indefinite period of time.. All subjects will receive PRM-151 10 mg/kg IV Days 1, 3, 5 then every 4 weeks in the extension. Dosing on days 1, 3 and 5 will be repeated every 28 weeks during the extension. PROs, PFTs, spirometry and 6MWT will be done every 4 weeks for the first 24 weeks and then every 12 weeks. DLco, FRC & TLC by nitrogen washout method will be done every 12 weeks. HRCT will be done at 1.5 years (Week 76) and 2.5 years (Week 128) on the same day as DLco and FRC & TLC by nitrogen washout. Subjects are allowed to begin treatment with, restart treatment with or increase the dose of pirfenidone or nintedanib after the week 28 visit have been performed

4.1.5.

4.1.6. Study Duration

Subjects will receive study drug for a minimum of 24 weeks. Subjects will participate in the study for up to 128 weeks, including a 4-week screening period, 24 week treatment period, an open-label treatment extension period for an indefinite period of time, and a 4 week follow up period.

5. SELECTION OF STUDY POPULATION

5.1. Study Population

5.1.1. Inclusion Criteria

Each subject must meet all of the following inclusion criteria to be enrolled in the study:

1. Subject must be 40-80 years of age at the time of signing the Informed Consent Form (ICF);
2. Subject has well documented IPF satisfying the ATS/ERS/JRS/ALAT diagnostic criteria (Raghu, Collard et al. 2011). In the absence of a surgical lung biopsy, HRCT must be “consistent with UIP” defined as meeting either criteria A, B, and C, or criteria A and C, or criteria B and C below:
 - A. Definite honeycomb lung destruction with basal and peripheral predominance.
 - B. Presence of reticular abnormality AND traction bronchiectasis consistent with fibrosis with basal and peripheral predominance.
 - C. Atypical features are absent, specifically nodules and consolidation. Ground glass opacity, if present, is less extensive than reticular opacity pattern.
3. If on pirfenidone or nintedanib, subject must have been on a stable dose of pirfenidone or nintedanib for at least 3 months prior to screening without increase in FVC% predicted on two consecutive PFTs, including screening PFTs. Subjects may not be on both pirfenidone and nintedanib.
4. If not currently receiving pirfenidone or nintedanib, subject must have been off pirfenidone or nintedanib for ≥ 4 weeks prior to screening
5. Subject has a FVC $\geq 50\%$ and $\leq 90\%$ of predicted.
6. Subject has an Hb corrected and/or Hb uncorrected DLCO $\geq 25\%$ and $\leq 90\%$ of predicted.
7. Minimum distance on 6MWT of 150 meters.
8. Subject has a forced expiratory volume in 1 second (FEV₁)/FVC ratio > 0.70 .
9. Women of child bearing potential (WCBP), defined as a sexually mature woman not surgically sterilized or not post-menopausal for at least 24 consecutive months if ≤ 55 years or 12 months if > 55 years, must have a negative serum pregnancy test within four weeks prior to the first dose of study drug and must agree to use highly effective methods of birth control throughout the study and up to 30 days after the study for WOCBP and up to 90 days for partners of child bearing potential of male participants. Highly effective methods of contraception include combined (estrogen and progestogen containing) hormonal contraception associated with inhibition of ovulation by oral, intravaginal, or transdermal administration; progestogen-only hormonal contraception associated with inhibition of ovulation by oral, injectable, or implantable administration; intrauterine device (IUD); intrauterine hormone-releasing system (IUS); bilateral tubal occlusion; partner vasectomy, and total abstinence (only if total abstinence is the preferred method and usual lifestyle of the subject). Adequate contraceptive use should be continued until 28 days after the final dose of the study drug.

-
10. Subject has a life expectancy of at least 9 months
 11. Subject, according to the investigator's best judgment, can comply with the requirements of the protocol.
 12. Subject and the treating physician considered all medicinal treatment options and / or possibly a lung transplantation prior to considering participation in the study
 13. If the subject is on a lung transplant list, the Investigator anticipates the subject will complete the study prior to transplant.
 14. Subject has provided written informed consent to participate in the study.

5.1.2. Exclusion Criteria

Subjects meeting any of the following exclusion criteria are not to be rolled in the study:

1. Subject has emphysema $\geq 50\%$ on HRCT or the extent of emphysema is greater than the extent of fibrosis according to the reported results of the most recent HRCT.
2. Subject has a history of cigarette smoking within the previous 3 months.
3. Subject has received investigational therapy for IPF within 4 weeks before baseline.
4. Subject is receiving systemic corticosteroids equivalent to prednisone > 10 mg/day or equivalent within 2 weeks of baseline.
5. Subject received Immuno-suppressants (e.g. azathioprine, cyclophosphamide, or cyclosporine or other immunosuppressants including those used after organ transplant) within 4 weeks of baseline. Subject has a history of a malignancy within the previous 5 years, with the exception of basal cell skin neoplasms. In addition, a malignant diagnosis or condition first occurring prior to 5 years must be considered cured, inactive, and not under current treatment.
6. Subject has any concurrent condition other than IPF that, in the Investigator's opinion, is unstable and/or would impact the likelihood of survival for the study duration or the subject's ability to complete the study as designed, or may influence any of the safety or efficacy assessments included in the study.
7. Subject has baseline resting oxygen saturation of $< 89\%$ on room air or with supplemental oxygen.
8. Subjects that are unable to refrain from use of the following:
 - a. Short acting bronchodilators on the day of and within 12 hours of pulmonary function, DLco, and 6-minute walk assessments.
 - b. Long acting bronchodilators on the day of and within 24 hours of these assessments.
9. Subject has a **known** post-bronchodilator (short-acting beta agonist [SABA] – albuterol or salbutamol) increase in FEV₁ of $>10\%$ and in FVC of $>7.5\%$.
10. Female pregnant and/or lactating subject.

5.2. Withdrawal and Replacement of Subjects

The Investigator may withdraw a subject from the study for any of the following reasons:

- Subject, Investigator, or Sponsor request.
- Protocol violation.
- AE.
- Pregnancy (mandatory).
- Progression of disease that, in the opinion of the Investigator, precludes further study drug treatment.
- Subject decision. A subject may withdraw consent to participate in the study at any time.

The reason for study withdrawal is to be documented in the subject's source documents and electronic case report form (eCRF).

5.3. Study Termination

If the Sponsor or Investigator discovers conditions arising during the study that suggest the study should be halted, then this can happen only after appropriate consultation between the Sponsor and Investigator. Conditions that may warrant study termination include, but are not limited to:

- The discovery of any unexpected, significant, or unacceptable risk to the subjects enrolled in the study.
- Site-specific inability of an Investigator to enter subjects at an acceptable rate.
- Insufficient adherence to the protocol requirements.
- A decision on the part of the Sponsor to suspend or discontinue development of study drug.
- A decision on the part of the Sponsor to suspend or discontinue the study for administrative reasons.

5.4. Subject Management

This study will be conducted on an out-patient basis.

Subjects will be evaluated for study eligibility during the Screening period within 4 weeks before the first study drug dose. All subjects must provide written informed consent before any study specific samples are collected or evaluations performed in this study.

Subjects who are determined to be eligible for the study will be enrolled and randomly assigned to treatment at Baseline (Week 0). For the purposes of this study, enrollment is defined as randomization.

Subjects are allowed to begin treatment on pirfenidone or nintedanib after week 28 visit is performed. .

During the 24-week treatment period, subjects are to attend study center visits on Days 1, 3 and 5 then an every 4-week basis at Weeks 4, 8, 12, 16, 20, and 24 (± 3 days) for study-related efficacy assessments and dosing.

After completing treatment through week 24, subjects will be offered the option to continue PRM-151 in an open-labeled treatment extension for an indefinite period of time.

An End of Study visit is to be conducted 4 weeks (± 3 days) after the last dose of study drug (Week 28 for the main study and upon completion for the open label extension).

5.5. Investigator Compliance

Study centers that deviate significantly from the protocol without prior approval from the Sponsor and regulatory authorities may be discontinued from the study. The Investigator at each study center is responsible for ensuring the accuracy and completeness of all research records, the accountability of study drug, and the conduct of clinical and laboratory evaluations as outlined in the protocol.

5.6. Subject Adherence

All subjects are required to adhere to the protocol-specified visit schedule. If a subject misses a scheduled visit, attempts should be made to reschedule the visit within the visit windows described above. Failure to attend scheduled study visits may result in discontinuation from the study.

5.7. Data Monitoring Committee

A blinded DMC will be established to review safety data from this study, thereby better ensuring the safety of study participants. Consistent with US Food and Drug Administration (FDA) recommendations (FDA Guidance for Industry, Establishment and Operation of Clinical Trial Data Monitoring Committees, 2006), the DMC will be constituted of independent clinicians' expert in the field of IPF and clinical research. A formal charter will be established for the conduct of the DMC.

The committee is planned to review the safety data in a blinded manner, but a procedure will be in place to allow the committee an immediate unblinding of either specific cases or of the whole study in case of detection of a potential safety signal necessitating an unblinded review of some (or all) subjects.

6. STUDY TREATMENT(S)

6.1. Investigational Product

All study drugs are for investigational use only and are to be used only within the context of this study. All study drugs will be supplied by Promedior.

6.2. Treatment(s) Administered

Subjects will be randomized to receive the study drug PRM-151 or placebo. Subjects randomized to placebo will receive intravenous (IV) infusions of sterile saline solution over 60 minutes. Please refer to the Pharmacy Manual for more detail.

Subjects randomized to study drug will receive intravenous (IV) infusions of 10 mg/kg PRM-151 over 60 minutes, with dose based on the subject's baseline weight. Refer to the Pharmacy Manual and the Investigator's Brochure for detailed instructions on special precautions and handling and requirements for weight based dose recalculations.

On all dosing days, dosing will occur *after* all safety and efficacy assessments scheduled for that visit are completed

Medical personnel authorized by the Investigator will be responsible for the administration of study drug and for observation of each subject throughout the study. Subjects should be observed for one-hour post infusion to monitor for infusion related reactions.

In the case of occurrence of signs and symptoms consistent with infusion related reaction, follow institutional protocol and reduce the rate of infusion of PRM-151 to half the initial rate; consider discontinuing infusion of PRM-151 if symptoms do not respond immediately to medical intervention. If signs and symptoms do not resolve immediately by slowing the infusion, discontinue infusion of PRM-151. If signs and symptoms resolve with intervention including discontinuation of PRM-151, PRM-151 infusion may be restarted at half the initial rate.

In the event of an infusion related reaction (IRR) beginning after treatment on Baseline, an ECG is performed and a blood sample for cytokines is collected as soon as possible after stabilization of the subject.

If PRM-151 resulted in an infusion related reaction, during a prior administration, use the following premedication for all subsequent PRM-151 administration:

- Diphenhydramine 50 mg IV or clemastine 2 mg IV or an equivalent dose of an antihistaminic drug
- Dexamethasone 10 mg IV or an equivalent dose of long-acting corticosteroid

No other dose modifications are required per protocol. The investigator should use his/her medical judgment in the case of adverse events that may require a dose interruption. If the subject is not able to adhere to the original dosing schedule, the subject should be dosed as soon as possible within 2 weeks of the scheduled visit. If the subject dosing is >2 weeks sponsor should be consulted.

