In the event of acute hypersensitivity or other infusion reaction, institutional protocol should be initiated, ECG should be performed, and a blood sample drawn for cytokines. Signs and symptoms of an infusion reaction may include the following: headache, fever, facial flushing, pruritis, myalgia, nausea, chest tightness, dyspnea, vomiting, erythema, abdominal discomfort, diaphoresis, shivers, hypertension, hypotension, lightheadedness, palpitations, urticaria and somnolence. Although unlikely, serious allergic reactions (e.g., anaphylaxis) may occur at any time during the infusion.

In the case of Grade 2 occurrence of signs and symptoms consistent with infusion related reaction, follow institutional protocol and reduce the rate of infusion of PRM-151 to half the initial rate; consider discontinue infusion of PRM-151 if symptoms do not respond to medical intervention. If signs and symptoms resolve with intervention including discontinuation of PRM-151, PRM-151 infusion may be restarted at half the initial rate.

In the case of Grade 3 or greater occurrence of signs and symptoms consistent with infusion related reaction, discontinue infusion of PRM-151.

In the event of an infusion related reactions, an ECG should be performed and a blood sample for cytokines should be collected as soon as possible after stabilization of the subject.

If PRM-151 resulted in signs and symptoms consistent with Grade 2 or 3 Infusion related reaction, infuse PRM-151 over 120 minutes and use the following premedication for all subsequent PRM-151 administration:

- Diphenhydramine 50 mg IV or clemastine 2 mg IV (or an equivalent dose of an antihistaminic drug)
- Dexamethasone 10 mg IV (or an equivalent dose of a long acting corticosteroid)

Infusion related reactions must be reported to Promedior as described in section 7.12.4.1, Reporting of Adverse Events of Special Interest.

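### Protocol 6.2 and 7.12.1.2 give different instructions for a Grade 3 or greater infusion reaction, and neither says which governs

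*Protocol*

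**What the plan says.** **Protocol 6.2 (Treatment(s) Administered)** sets one sequence for any infusion related reaction and names no grade.

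- First action: "In the case of occurrence of signs and symptoms consistent with infusion related reaction, follow institutional protocol and reduce the rate of infusion" to half its initial value.
- Discretionary stop: consider stopping if there is no immediate response to medical intervention.
- Mandatory stop: "If signs and symptoms do not resolve immediately by slowing the infusion, discontinue infusion of PRM-151".
- Restart: "If signs and symptoms resolve with intervention including discontinuation of PRM-151, PRM-151 infusion may be restarted at half the initial rate".
- Later infusions: "If PRM-151 resulted in an infusion related reaction, during a prior administration, use the following premedication for all subsequent PRM-151 administration". The antihistamine and dexamethasone doses follow.

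The section then says that the protocol requires no further dose modification, and leaves interruptions for adverse events to the investigator's judgment.

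**Protocol 7.12.1.2 (Infusion related reactions)** is graded.

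- Grade 2: halve the rate, then "consider discontinue infusion of PRM-151 if symptoms do not respond to medical intervention". Restart at half rate is allowed after resolution.
- Grade 3 or greater: "In the case of Grade 3 or greater occurrence of signs and symptoms consistent with infusion related reaction, discontinue infusion of PRM-151". No slowing step and no restart sentence follow.
- Later infusions: "If PRM-151 resulted in signs and symptoms consistent with Grade 2 or 3 Infusion related reaction, infuse PRM-151 over 120 minutes", with the same premedication as in 6.2.

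Its only section reference is to 7.12.4.1, for reporting. SAP 4.2.3 and 5.2.6.3 describe and tabulate reactions but contain no stop rule.

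**The concern.** Both sections are current text, and both tell site staff what to do while a reaction is happening. For a severe reaction they prescribe different first actions. A nurse or investigator working from the treatment section has no pointer to the graded rule 30 or so subsections later, and the statement closing 6.2's dosing rules suggests that nothing further applies.

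What is at stake is patient safety and consistent conduct. Under 6.2 as written, a Grade 3 reaction that settles on slowing is infused to completion at half rate. Under 7.12.1.2 the infusion stops. By its wording, the slow-first step in 6.2 covers even Grade 4, which Table 7-2 defines as life-threatening. Monitoring is also hampered, because a site that follows 6.2 to the letter can deviate from 7.12.1.2.

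The exposure does not end at Week 28. In the extension, "All subjects will receive PRM-151 10 mg/kg IV Days 1, 3, 5 then every 4 weeks in the extension".

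**Working it through.** The protocol gives no figure for this point, so the check is a clause-by-clause comparison, followed by a rough sizing.

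**Comparison.** The test is whether one action can satisfy both sections.

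| Situation | 6.2 | 7.12.1.2 | Both satisfied? |
|---|---|---|---|
| Grade 1 | Halve rate; stop if slowing fails | No grade-specific action | Yes, follow 6.2 |
| Grade 2, settles on slowing | Half rate | Half rate | Yes |
| Grade 2, slowing fails | Stop | Silent on failed slowing; consider stopping if medical intervention fails | Yes, by stopping (gap) |
| Grade 3 or greater, first action | Halve rate | Discontinue | **No** |
| Grade 3 or greater, settles on slowing | Half rate continues | Discontinued | **No** |
| Grade 3 or greater, slowing fails | Stop after trying | Stop at once | Same end, different timing |
| Same-day restart after Grade 3 or greater | Permitted at half rate | Silent | Yes, by not restarting (gap) |
| Later infusions, Grade 2 or 3 | Premedicate | Premedicate, 120 minutes | Yes, do both |
| Later infusions, Grade 1 or 4 | Premedicate | Silent | Yes, follow 6.2 |

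The sections are incompatible only at Grade 3 or greater. Elsewhere one section is silent where the other speaks. No sentence in either document sets precedence.

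**Exposure.**

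- Double-blind infusions per subject: Days 1, 3 and 5, plus Weeks 4, 8, 12, 16, 20 and 24, so 3 + 6 = 9.
- Active arm: 78 × 9 = 702.
- Both arms: 117 × 9 = 1,053. Placebo counts because site staff other than the pharmacist are blinded (6.4) and would handle a suspected reaction the same way.
- Extension: 3 + 6 = 9 infusions per subject per 28-week cycle.

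**Frequency.** The documents give no expected rate for this trial. Earlier subjects treated with PRM-151:

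- Myelofibrosis: 2 reactions (1.2), taken over the 27 subjects in 1.5. Section 1.2 calls them Grade 2; 1.5 calls them mild.
- IPF: 0 reactions (1.2) in 15 subjects (1.4).
- Any grade, pooled: 2/(27 + 15) = 2/42 = 4.8%, exact 95% CI 0.6% to 16.2%. Applied to 78 active subjects: about 3.7 (0.5 to 12.6).
- Grade 3 or greater, pooled: 0/42. Upper limit of the exact 95% interval: 1 − 0.025^(1/42) = 8.4%; 78 × 0.0841 = 6.6 subjects.
- Grade 3 or greater, IPF only: 0/15. Upper limit: 1 − 0.025^(1/15) = 21.8%; 78 × 0.218 = 17.0 subjects.

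The upper limits show how little the data exclude and are not forecasts. Pooling assumes a common rate across two diseases and different schedules. The IPF study also infused over 30 minutes, against 60 here.

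**The case against.** The strongest reply is that the graded text, under its own heading, is naturally read as the specific rule that overrides the general one. A careful clinician would stop for a Grade 3 reaction anyway, and 6.2's reliance on investigator judgment permits it. Both sections defer to institutional protocol. There are further safeguards: vital signs every 15 minutes during infusion (7.8), an hour of observation afterwards (6.2), 24-hour reporting of every suspected reaction whatever its severity (7.12.4.1), and DMC safety review (5.7). Where slowing fails, both sections end in a stop.

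Much of this stands. It narrows the practical divergence to severe reactions that settle on slowing, and to the time spent trying to slow others. It does not remove the inconsistency. The protocol never says that the graded text prevails, and reading it that way would drop 6.2's mandatory stop for a Grade 2 reaction that slowing does not resolve. Reporting and DMC review also act after the event.

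A reader might infer that unresolved Grade 2 is a second direct contradiction, with 6.2 saying stop and 7.12.1.2 saying only consider stopping. The wording does not support that. The discretionary stop in 7.12.1.2 is triggered by no response to medical intervention, and 6.2 has a very similar sentence. On failure of slowing, 7.12.1.2 says nothing, so a site that stops obeys both. It is a gap, and it matters only if 7.12.1.2 is read alone.

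**Conclusion.** The point holds for Grade 3 or greater: two current sections prescribe different first actions, with no precedence statement. The missing Grade 2 stop in 7.12.1.2 is a related gap that constrains how the conflict can be repaired. This is a safety-conduct defect that should be corrected. It is not evidence that subjects have been harmed, and no Grade 3 or greater reaction is reported in the earlier data. That conclusion rests on the text alone and does not depend on the rough rates above.

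A reader might also infer a threat to the efficacy analysis, since the required dexamethasone premedication has no written exception in 7.9.1 and could lead to per-protocol exclusions. The documents do not establish this. An exception can be read as implied, deviations are adjudicated at blind review (8.3), and the Study Deviation Guidance Document cited in SAP 3.1.1 may already cover it. The primary analysis uses all treated subjects as randomized (SAP 3.2) and is not affected.

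**What to change.** Make 7.12.1.2 the single governing rule and replace the reaction-management text in 6.2 with a cross-reference to it. Before 6.2 is cut, 7.12.1.2 should say:

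- **Grade 1 or 2:** follow institutional protocol and halve the rate; consider discontinuing if there is no immediate response to medical intervention; discontinue if slowing does not bring immediate resolution; after resolution, restart at half the initial rate is allowed.
- **Grade 3 or greater:** discontinue at once, without slowing first.
- **Any reaction:** keep the ECG and cytokine sampling, and premedicate later infusions with the drugs and doses now named in 6.2.
- **After Grade 2 or 3:** also keep the 120-minute infusion.

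The clinical team should decide and state whether same-day restart is allowed after Grade 3, and whether any dosing follows Grade 4.

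Optionally, a sentence in 7.9.1 and 8.3 could say that premedication required by 7.12.1.2 is neither forbidden medication nor a major deviation. That is a clarification and not part of this defect.

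The cost is one rewritten paragraph, one cross-reference, two short clinical decisions and a site memo. No statistical analysis changes.
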